7.5 Safety Analyses

Summary tables and data displays will be provided for adverse events as well as serious adverse events (as detailed in the study protocol). Procedure-related complications in the endovascular recanalization group will be analyzed. The Chi-square test or Fisher's exact test will be used to compare the incidence of adverse events and serious adverse events between the treatment groups.

7.6 Propensity Score Matching Analysis

Propensity score matching (PSM)² will be performed to reduce the possible influence of selection bias and confounders on the outcomes. A PSM cohort will be established in a 1:1 ratio based on the nearest-neighbor matching algorithm with a caliper width of 0.2 of the propensity score with main variables associated with the primary outcome as covariates. Statistical analysis methods for baseline characteristics and outcome will remain consistent before and after PSM.

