3.16.5 Statistical Significance and Software

All statistical tests are performed by 2-sided tests. A 2-sided P value less than 0.05 is considered to demonstrate a statistically significant difference. All analyses will be performed with SAS software version 9.4 (SAS Institute).

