7.4 Demographic and Baseline Characteristics

The following demographic information baseline characteristics, such as age, sex, medical history, smoking history, alcohol history, treatment history, qualifying ischemic event characteristics, Alberta Stroke Program Early CT Score (ASPECTS) for anterior circulation stroke as well as posterior circulation ASPECTS (pc-ASPECTS), baseline mRS score and NIHSS score, will be listed and summarized for subjects in each treatment group.

The continuous data followed normal distribution will be presented as mean and standard deviation, and the continuous data followed skewness distribution will be presented as median and interquartile range; categorical data will be presented as n (%). T-test or Wilcoxon-Mann-Whitney test will be used for comparison between two continuous data, and Chi-squared tests, Fisher exact test will be used for comparison between two categorical data.

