7.5 Primary Efficacy Outcome

The difference in primary outcome between groups was assessed using Kaplan-Meier analysis and compared via log-rank test. Hazard ratio (HR) between the two groups and its 95% CI will be calculated using a Cox proportional hazards regression model. Furthermore, a multivariate Cox proportional hazards model will be used to perform multivariable adjustment for the primary outcome, yielding the adjusted hazard ratio (aHR) and its 95% CI.

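### The matched cohort inherits unpaired methods: its unadjusted Cox interval is about right to moderately too wide, and significance tests, the only balance check named, can miss residual imbalance

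*SAP*

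**What the plan says.** Treatment is chosen by the patient or a legal representative (Protocol 3.6, SAP 4). The plan names two tools against the resulting selection bias: a multivariable Cox model and propensity score matching.

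On matching, SAP 7.6 (Propensity Score Matching Analysis) says "A PSM cohort will be established in a 1:1 ratio based on the nearest-neighbor matching algorithm". The closeness required of a match is given only as "caliper width of 0.2 of the propensity score". It then adds "Statistical analysis methods for baseline characteristics and outcome will remain consistent before and after PSM". Protocol 3.16.4 carries the same text.

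The methods that this sentence carries into the matched cohort are:

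- Baseline, continuous (SAP 7.4): "T-test or Wilcoxon-Mann-Whitney test will be used for comparison between two continuous data".
- Baseline, categorical (SAP 7.4): "Chi-squared tests, Fisher exact test will be used for comparison between two categorical data".
- Primary outcome (SAP 7.5, Primary Efficacy Outcome): "The difference in primary outcome between groups was assessed using Kaplan-Meier analysis and compared via log-rank test" and "Hazard ratio (HR) between the two groups and its 95% CI will be calculated using a Cox proportional hazards regression model", followed by a multivariable Cox model whose covariates are not listed.
- Other outcomes (SAP 7.7, Secondary Outcomes): Cox, logistic, ordinal logistic and linear models.

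Neither document names a paired test, a variance clustered on the pair, a standardised mean difference (SMD), a balance limit, the scale of the caliper or an expected number of pairs.

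**The concern.** Two patients matched on the propensity score resemble each other in the variables that went into the score. If those variables predict the outcome, outcomes within a pair are correlated, and a standard error computed as if the groups were independent is not the right one for the matched estimate.

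Balance is a separate matter. A P value for a baseline difference depends on sample size as well as on the difference. Matching discards patients, so P values can rise without any gain in balance. A reader of a matched baseline table that holds only P values cannot tell whether confounding has been removed.

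The matched hazard ratio is one of only two protections against self-selection in this study. At stake are the precision of that estimate and whether a reader can judge if the matching worked.

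**Working it through.** **Inputs.** From the documents: 1:1 nearest-neighbour matching, a caliper of 0.2 on an unstated scale, the unpaired tests above, 1 year of follow-up, and a two-sided 0.05 level (Protocol 3.16.5: "A 2-sided P value less than 0.05 is considered to demonstrate a statistically significant difference"). The documents give no sample size, event rate, number of pairs or balance limit, so there is no stated figure to reproduce and ranges are shown.

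**Step 1: what a significance test can miss.** With n pairs and an unpaired test, the largest sample SMD that still gives P>0.05 is about 1.96 × √(2/n). The chance of missing a true SMD of 0.2 is one minus the power of the two-sample t-test.

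| Pairs | Largest SMD with P>0.05 | Chance of missing a true SMD of 0.2 |
|---|---|---|
| 50 | 1.96 × √(2/50) = 0.392 | 83% |
| 100 | 1.96 × √(2/100) = 0.277 | 71% |
| 150 | 1.96 × √(2/150) = 0.226 | 59% |
| 300 | 1.96 × √(2/300) = 0.160 | 31% |

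For P=0.05 to correspond to an SMD of 0.1, n = 2 × (1.96/0.1)² = 768.3, so about 769 pairs. These are limits of detection, not forecasts of the imbalance that matching will leave.

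**Step 2: what matching may leave.** This was simulated, and every setting is an assumption: greedy 1:1 matching without replacement, four covariates, 150, 300 or 600 patients with half treated, log-odds of treatment 0.7 per SD of the confounder score, baseline hazard 0.18 per year, true hazard ratio 1, and 1,500 runs per setting. The table uses a prognostic log hazard ratio of 1.0 per SD.

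| Caliper | Pairs | Largest SMD >0.1 | All four t-tests P>0.05 | Bias in log HR | Type I error, unpaired / pair-robust |
|---|---|---|---|---|---|
| 0.2 SD of the logit | 51 | 59% | about 100% | 0.006 | 0.029 / 0.045 |
| 0.2 SD of the logit | 107 | 22–23% | about 100% | 0.002–0.013 | 0.031–0.037 / 0.048–0.058 |
| 0.2 SD of the logit | 219 | 3% | about 100% | 0.009 | 0.030 / 0.047 |
| 0.2 on the raw score | 59 | 95% | about 100% | 0.132 | 0.038 / 0.055 |
| 0.2 on the raw score | 122 | 94% | about 100% | 0.157 | 0.072 / 0.093 |
| 0.2 on the raw score | 248 | 93% | 94% | 0.166 | 0.119 / 0.154 |

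On the raw score, the bias turns a true hazard ratio of 1 into exp(0.132) = 1.14 to exp(0.166) = 1.18. Its direction follows from the assumed confounding. In nearly all of these runs the t-tests raised no alarm.

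**Step 3: the standard error.** Same simulation with the logit caliper, and about 107 or 219 pairs. The figures are the mean model SE divided by the empirical SE.

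| Prognostic log HR per SD | Unpaired Cox SE ratio | Type I error, unpaired | Pair-robust SE ratio |
|---|---|---|---|
| 0 | 1.00–1.01 | 0.041–0.045 | 1.00–1.01 |
| 0.5 | 0.99–1.01 | 0.036–0.043 | 0.98–0.99 |
| 1.0 | 1.04–1.08 | 0.030–0.037 | 0.97–1.00 |
| 1.5 | 1.17 | 0.020–0.024 | 1.00–1.01 |

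The unpaired SE is about right when the covariates predict the outcome weakly and becomes too large as they predict it strongly. It was clearly too small in only one setting (ratio 0.94, raw-score caliper, about 20 events), and there the pair-robust SE was equally low (0.93).

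**The case against.** The case against acting has four parts.

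- **The interval error is conservative.** A reader might infer that ignoring the pairs makes the matched interval too narrow or creates false positives. The calculations do not support this: type I error attributable to the unpaired SE fell below 5%. The excess under the raw-score caliper comes from bias. This part of the objection stands in full.
- **No pass rule is written.** A reader might infer that the plan accepts a match when every baseline P value exceeds 0.05. Neither document says so. They only repeat the baseline tests after matching. This also stands, but those tests remain the only balance information the plan promises.
- **Large undetected imbalance need not occur.** With a caliper of 0.2 SD of the logit, a largest SMD above 0.2 was seen in 9% of passing runs at about 51 pairs and 1% at about 107. So the claim can only be that the tests can pass residual imbalance, not that they do. The reassurance depends on a caliper scale that the plan does not state.
- **The planned multivariable Cox model also carries over.** In further runs under similar assumptions (400 per setting, 400 or 600 patients), the ordinary Cox model adjusted for the matching covariates had an SE 0.94 to 1.01 times the empirical SE, type I error of 0.04 to 0.075 and log HR bias of at most about 0.03. With the raw-score caliper, the unadjusted bias in those runs was 0.10 to 0.25. This is a real mitigation. It requires that the adjustment set include the matching variables, which the plan does not say, and it does not help the unadjusted matched hazard ratio and log-rank test.

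**Conclusion.** The point holds in moderate form. The plan expressly carries independent-sample methods into a matched cohort and offers no diagnostic suited to judging the match.

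For the unadjusted matched Cox interval, the SE is roughly 0% to 17% too large, with type I error of about 2% to 4.5%. That costs some precision and is negligible if the covariates are weak predictors. For balance, sample SMDs of about 0.39, 0.28, 0.23 and 0.16 can go unflagged at 50, 100, 150 and 300 pairs. The most consequential element is the unstated caliper scale. If 0.2 is applied to the raw score, an SMD above 0.1 is usual and the unadjusted matched hazard ratio is biased. A pair-robust SE does not cure that, whereas a tighter caliper or covariate adjustment does.

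The limits of detection follow from the formula alone. All simulated figures rest on assumed inputs, because the documents supply none. This should be corrected before analysis, but it does not by itself invalidate the matched comparison.

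**What to change.** Replace the sentence on unchanged methods in Protocol 3.16.4 and SAP 7.6 (Propensity Score Matching Analysis) with text that does the following:

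1. Judges matched balance by standardised mean differences against a prespecified limit, for example 0.1, and includes any covariate above it in the matched-cohort outcome model.
2. States the caliper as 0.2 SD of the logit of the propensity score.
3. Estimates the matched hazard ratio by a Cox model with variance clustered on the matched pair (PROC PHREG with COVS(AGGREGATE) and an ID statement for the pair), and takes the matched P value from that model. Kaplan-Meier curves can stay as they are.
4. Uses pair-clustered variances (GEE or robust) for the binary, ordinal and continuous outcomes. Conditional models are not a substitute, because they estimate a conditional effect and not the marginal one.

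The cost is new wording and slightly more programming; no new data are needed. There are two limits. The robust SE can be slightly too small with very few events (ratio 0.93 at about 20 events). It also does not correct bias from poor matching: with the raw-score caliper and about 248 pairs, it raised type I error from 0.12 to 0.15. Items 1 and 2 therefore matter more than items 3 and 4.

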7.7 Concomitant Medication and Risk Factor Management

Describe the list of concomitant medications, including antiplatelet drugs (aspirin, clopidogrel, ticagrelor, cilostazol), anticoagulants, lipid-lowering agents (such as statins), and so on. Additionally, outline the management of risk factors, which includes blood pressure, low-density lipoprotein cholesterol (LDL-C), high-density lipoprotein cholesterol (HDL-C), triglycerides, total cholesterol, and hemoglobin A1c (HbA1c). Lifestyle factors to be considered include BMI, smoking status, alcohol consumption, and regular moderate physical exercise. Chi-squared tests or Fisher's exact test will be employed to compare the numbers between treatment groups.

8. Reference

